### *Safety Follow-Up Visit*

The mandatory Safety Follow-Up Visit should be conducted approximately 30 days after the last dose of trial treatment. All AEs that occur prior to the Safety Follow-Up Visit should be recorded. Subjects with an AE of Grade > 1 will be followed until the resolution of the AE to Grade 0-1 or until the beginning of a new anti-neoplastic therapy, whichever occurs first. SAEs that occur within 30 days of the end of treatment or before initiation of a new anti-cancer treatment should also be followed and recorded.

### Survival Follow-up

Once a subject experiences confirmed disease progression or starts a new anti-cancer therapy, the subject moves into the survival follow-up phase for 24 months and should be contacted by telephone every 12 weeks to assess for survival status until death, withdrawal of consent, or the end of the study, whichever occurs first.

## 6.6 Calendar

	Screening within 28 days of CID1	Cycle 1 Day 1 ± 2 days	Cycle 2 day 1 ± 2 days and subsequent cycles	Cycle 3 day 1 ± 5 day and every 3 rd cycle thereafter	EOT m	Safety Follow-Up Visit ± 7 days n	Post-Progression Follow-up j

Complete History/Physical a	X				X		
History & Assessment b		X	X			X	
Toxicity Notation		X	X		X	X	
ECOG	X	X	X		X	X	
ECG	X						
Tumor Measurement/Disease Assessment c	X			X	X		
Hematology d	X	X	X		X		
Chemistry e	X	X	X		X		
Coagulation f	X						
Urinalysis g	X						
TSH, free T4	X			X			
CEA	X			X			
Hepatitis Screening h	X						
Serum/urine Pregnancy, if applicable i	X						
Survival f/u j							X
██████████	■						
██████████							
██████████	■			■			
██████████							

- a. Complete medical history and physical examination including demographics, surgery, therapies, medications, smoking, alcohol history, co-existing diseases, allergy, NYHA classification, vital signs (heart rate, respiration rate, temperature and BP), height, weight and review of systems. A full physical exam should be performed during screening.
- b. History and assessment including brief examination, vital signs and review of systems. Note all toxicities and adverse events, using CTCAE version 4.03 and in accordance with section 9.1. The investigator or qualified designee will also perform a directed physical exam as clinically indicated prior to each treatment cycle administration.
- c. Tumor assessment using CT or MRI (chest, abdomen, pelvis) (at investigator's discretion) will be collected at screening, after every 3 cycles, and as clinically indicated. Tumor response will be assessed using RECIST 1.1 and irRC criteria. Tumor measurement/disease assessment should be performed within 7 days at the beginning of every 3rd cycle.
- d. Hemoglobin, hematocrit, red blood cell count, white blood cell count with differential (neutrophils, bands, lymphocytes, monocytes, eosinophils and basophils) and platelet count.
- e. ALT, AST, alkaline phosphatase, total bilirubin, direct bilirubin, LDH, creatine kinase, lipase, amylase, glucose, calcium, phosphate, magnesium, bicarbonate, sodium, potassium, chloride, creatinine, blood urea nitrogen (BUN), total protein and albumin.

- f. PT-INR and aPTT.
- g. Urinalysis including blood, glucose, protein, specific gravity
- h. Hepatitis B surface antigen, surface antibody, and Hepatitis C antibody
- i. Pregnancy test will be performed at baseline for WOCBP and then only as clinically indicated
- j. After off treatment following disease progression survival f/u, can be performed over the phone every 3 months
- k. Archival tissues ( 10 unstained slides) if available
- l. The PBMC should be viably frozen (for flow cytometric analysis) and the plasma frozen separately .The actual analyses used will be based on response and determined by the investigator at a later date. Two green top (Sodium Heparin) tubes (about 20 ml) will be used each time. This will ONLY be collected at the screening and at the beginning of the 3rd cycle.
- m. If a subject discontinues treatment due to confirmed PD, only the EOT disease assessment is required if it has been > 4 weeks since the last disease assessment
- n. The safety follow-up visit will be approximately 30 days after the last dose or prior to the start of a subsequent anti-cancer therapy.

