## **Exploratory Objective**

1. To use the immunohistochemical stains and HTG EdgeSeq ImmunoOncology Assay to assess the host immune response in tumor microenvironment. The resulting “immune gene expression profiles and immune cells profiles” will be correlated with clinical outcome in a descriptive analysis.
2. To use the Luminex Multiplex immunoassay and the flowcytometry, to analyze the effect of this combination on the immune system and immune cells in peripheral blood.

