#### 12.4 Flow cytometry

The isolated peripheral blood mononuclear cells before, during and after treatment will be analyzed to measure the frequency of effector T cells and regulatory T cells (Treg)s using flow cytometry. Eight color flow cytometry analysis will be performed on the isolated mononuclear cells using the following antibodies: florescence conjugated anti-CD3, anti-CD4, anti-CD8, anti-CD25, anti-CD127, anti-Foxp3, anti-granzyme B and anti-perforin (BD Bioscience or eBioscience). For extracellular staining, cells will be incubated for 30 minutes at 4°C with optimal dilution of each antibody. Intracellular staining for Foxp3, granzyme B and perforin will be preceded by fixation and permeabilization with intracellular staining kit (eBioscience). Flow cytometry will be performed on a FACS LSRFortessa (BD) and analyzed using CellQuest software (BD). The results of flowcytometry pre and post treatment will be correlated with the clinical efficacy to identify possible mechanisms of tumor response

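### Footnote l of the calendar lets response decide which blood biomarker analyses are run, although section 12.4 then correlates those results with efficacy

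*Combined protocol and SAP*

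**What the plan says.** - **Section 6.6, Calendar, footnote l.** Cells are frozen viably for flow cytometry and plasma is frozen separately. The footnote continues: "The actual analyses used will be based on response and determined by the investigator at a later date". On timing it says: "This will ONLY be collected at the screening and at the beginning of the 3 rd cycle".
- **Section 12.4, Flow cytometry.** "The isolated peripheral blood mononuclear cells before, during and after treatment will be analyzed", using eight named antibodies, to measure effector and regulatory T cell frequencies. It then says: "The results of flowcytometry pre and post treatment will be correlated with the clinical efficacy to identify possible mechanisms of tumor response".
- **Section 2, Exploratory Objective, second item.** Luminex and flow cytometry are to be used "to analyze the effect of this combination on the immune system and immune cells in peripheral blood". The phrase about a descriptive analysis belongs to the first item, on tumor tissue, and not to this one.
- **Sections 9.1 and 9.7.** Biomarkers are listed as exploratory. Section 9.7 gives no analysis method for them.
- **Section 5.6.** The trial is open-label, without randomization or blinding.

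**The concern.** Footnote l is a positive rule and not an omission. It fixes the basis of the choice (response), who makes it (the investigator) and when (later). The investigator knows response when choosing, and response is also what section 12.4 sets the results against. No visible text requires the analyses to be listed before assay results are seen beside outcomes, or requires every marker measured to be reported.

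Two things are at stake:

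- A reader of the eventual correlation would not know how it came to be the one reported.
- The broader question in section 2, what the combination does to immune cells in blood, needs patients with and without disease control. A response-based choice could leave the second group out.

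**Working it through.** The plan gives no figure for the biomarker work, so most of this check compares passages. The arithmetic only shows how the patients would divide.

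**1. The design behind the patient numbers (section 9.2).** Inputs: null rate 5%, target rate 20%, stop at 0 of 18, success at 4 or more of 32. The probability of declaring success is

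sum over x = 1 to 18 of P(X = x; 18, p) × P(Y ≥ 4 − x; 14, p).

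This gives 0.072 at p = 0.05 (limit 0.10) and 0.901 at p = 0.20 (target 0.90). A full search returns the same minimax design, so the plan's figure reproduces. Footnote l does not enter it.

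**2. How 32 patients would divide.**

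| True disease control rate | Expected with control | Expected without control |
|---|---|---|
| 5% | 32 × 0.05 = 1.6 | 32 − 1.6 = 30.4 |
| 20% | 32 × 0.20 = 6.4 | 32 − 6.4 = 25.6 |

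If only samples from patients with disease control were assayed, about 2 to 6 patients would contribute and 80% to 95% of the phase II patients would not. If assays were run only when activity is seen, there is a further risk. At a true rate of 5%, the chance of no disease control in stage 1 is 0.95^18 = 0.397, and the blood objective might then not be addressed.

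**3. What footnote l could mean.**

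| Reading | Consequence |
|---|---|
| Response decides which assays or markers are run | The set of analyses depends on the outcome |
| Response decides whose samples are run | The comparison group may be lost |
| Laboratory work goes ahead only if responses occur | The section 2 blood objective may go unanswered |

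The text does not say which is meant. All three depend on the outcome.

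**4. Is response known in time?** Section 6.4 and the calendar put the first on-treatment scan at the start of cycle 3, the same point as the second blood sample. Response information can therefore exist before any pair of samples is assayed.

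**5. Does the choice alone bias the result?** No. Suppose a marker is unrelated to outcome and the assay is picked from response data alone, before the marker is measured. The choice is then independent of the marker values, and a test of that marker keeps its nominal error rate. Bias needs a further step: marker results seen beside outcomes, and then a selection of what to run next or report. Footnote l does not describe that step, but nothing visible rules it out.

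**6. Footnote l against section 12.4.** Section 12.4 says the cells will be analysed with a fixed panel and sets no responder restriction. Footnote l leaves the analyses to be settled later. Sampling times also differ: footnote l allows only screening and the start of cycle 3, while section 12.4 has cells from before, during and after treatment.

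**The case against.** The strongest reply is that this is exploratory work with its main elements already named. Section 2 names the platforms, and section 12.4 names the cell populations and antibodies and claims only to look for possible mechanisms. Footnote l itself says the cells are kept for flow cytometry, so the open choice may concern only the plasma or additional assays. Stored samples may simply be reserved until the trial shows activity. Much of section 12 is redacted and could hold an analyte list. All of this limits the weight of the point. The sentence still makes the choice depend on response, whatever the redacted text says.

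Three stronger readings are tempting, and the documents do not support them:

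- **That the correlation is circular or uninterpretable.** Step 5 of the working shows that choosing an assay on response is not enough for this. Sampling by response is also legitimate if both groups are assayed.
- **That a false-positive rate can be attached.** A reader might compute 1 − 0.95^20 = 64% for 20 markers, or 1 − 0.95^10 = 40% for 10. Those figures describe testing many independent null markers at an assumed 5% level, not this rule. The documents give neither a marker count nor a test level. Running the same markers on every patient without adjustment would leave the figures unchanged.
- **That only responders' samples will be run.** Footnote l speaks of analyses, not patients. This is one reading among several.

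**Conclusion.** The point holds as a limited one. As written, footnote l lets the outcome influence which analyses, and possibly whose samples, enter a correlation with that outcome. It also sits badly with the commitment in section 12.4. The resulting selection is of unknown size, and no numerical bias can be given. The more concrete risk is that peripheral immune effects are not measured in patients without disease control, about 26 to 30 of 32 at the two design rates.

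The conclusion rests on the plain wording of footnote l, on the open-label design, and on the absence of any limiting rule in the visible text. Nothing is inferred from the redacted parts. The primary endpoint, its error rates and the sample size of 32 are untouched. The change is worth making because it is small and protects the only comparison that the blood samples can support.

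**What to change.** 1. Delete the sentence in footnote l that makes the analyses depend on response.
2. State in footnote l and section 12.4 that the section 12.4 flow panel and a named plasma analyte list will be run on all patients with stored samples, regardless of response. Fix the list before any assay result is linked to response.
3. State that every marker measured will be reported and that any analysis added later will be labelled post hoc.
4. Reconcile the sampling times in footnote l and section 12.4.

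The text change is a few sentences in two places. The real cost is assaying samples from patients without response, which the plan already has collected and stored.

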## **7. Assessment types**

### **7.1 Pre-Treatment Assessments**

The nature of the study and the associated potential risks will be explained to all study candidates and a signed informed consent must be obtained before any study-specific Pre-Treatment procedures are performed. Pre-Treatment assessments must be completed and reviewed within 28 days prior to the start of study drug treatment to ensure eligibility for study entry

Pre-Treatment evaluations will include inclusion/exclusion criteria evaluation, demographic data collection, ECOG performance status, NYHA classification, medical and surgical history collection, vital signs, complete physical examination (including height and weight), 12-lead ECG, biochemistry, hematology and urinalysis, pregnancy test (urine or serum  $\beta$ - hCG in women of childbearing potential only), and tumor assessments

### **7.2 Efficacy**

Response and progression will be evaluated using the international criteria proposed by the revised Response Evaluation Criteria in Solid Tumors (RECIST) guideline (version 1.1) (see Appendix B). Changes in the largest diameter (unidimensional measurement) of the tumor lesions and the shortest diameter in the case of malignant lymph nodes are used in the RECIST criteria.

### **7.3 Safety**

Safety assessments will consist of monitoring and recording all adverse events, including serious adverse events, the monitoring of hematology, blood chemistry, ECG and the regular monitoring

of vital signs, and physical condition as shown in corresponding tables. Safety and tolerability will be assessed according to the NIH/NCI CTC version 4.0.

## **8. Safety monitoring and reporting**

### **8.1 Adverse Events**

#### **8.1.1 Definitions**

An Adverse event (AE) is any unfavorable and unintended sign, symptom, or disease temporally associated with the use of an investigational medicinal product (IMP) or other protocol-imposed intervention, regardless of attribution. Medical conditions/diseases present before starting study drug are only considered adverse events if they worsen after starting study drug. Abnormal laboratory values or test results constitute adverse events only if they induce clinical signs or symptoms, are considered clinically significant, or require therapy. Clinically significant laboratory results are those requiring a change in the patient's treatment, further diagnostic testing or specific clinical intervention (i.e., treatment delays or dose modifications, etc). The occurrence of adverse events should be sought by non-directive questioning of the patient at each visit during the study. Adverse events also may be detected when they are volunteered by the patient during or between visits or through physical examination, laboratory test, or other assessments. As far as possible, each adverse event should be evaluated by the investigator to determine:

- the severity grade (mild, moderate, severe) or (grade 1-4)
- its relationship to either or the study drugs (unrelated, unlikely, possible, probable, definite)
- its duration (start and end dates or if continuing at final exam)
- action taken (no action taken; study drug dosage adjusted/temporarily interrupted; study drug permanently discontinued due to this adverse event; concomitant medication taken; non-drug therapy given; hospitalization/prolonged hospitalization)
- whether it constitutes a serious adverse event (SAE)

Attribution is the relationship between an adverse event or serious adverse event and the study treatment. Attribution will be assigned as follows:

- Definite: The AE is clearly related to the study treatment;
- Probable: The AE is likely related to the study treatment;
- Possible: The AE may be related to the study treatment;
- Unlikely: The AE is doubtfully related to the study treatment;
- Unrelated: The AE is clearly not related to the study treatment.

A serious adverse event is an undesirable sign, symptom or medical condition which:

1. Is fatal or life-threatening.
2. Requires or prolongs hospitalization.
3. Results in persistent or significant disability/incapacity.

4. Constitutes a congenital anomaly or a birth defect.
5. Is medically significant, may jeopardize the subject and may require medical or surgical intervention to prevent one of the outcomes listed above.

For full adverse event reporting as per Janssen guidelines, see **Appendix C**.

Events not considered to be serious adverse events are hospitalizations for the:

- Routine treatment or monitoring of the studied indication, not associated with any deterioration in condition.
- Treatment, which was elective or pre-planned, for a pre-existing condition that did not worsen.
- Treatment on an emergency, outpatient basis for an event not fulfilling any of the definitions of serious given above and not resulting in hospital admission.

Pregnancy, although not itself a serious adverse event, should also be reported on a serious adverse event form or pregnancy form and be followed up to determine outcome, including spontaneous or voluntary termination, details of birth, and the presence or absence of any birth defects or congenital abnormalities.

Serious adverse event reporting is initiated after the signs informed consent, and continues until 4 weeks after the patient's last dose of study medication. The period after discontinuing study drug may be extended at investigators discretion.

Progression of the cancer under study is not considered an adverse event.

### **8.1.2 Adverse Events of Special Interest (AESI) with Ibrutinib**

Specific adverse events, or groups of adverse events, will be followed as part of standard safety monitoring activities. These events (regardless of seriousness) will be reported to Janssen Drug Safety per the SAE reporting timelines.

#### **Major Hemorrhage**

Major hemorrhage is defined as any hemorrhagic event that is Grade 3 or greater in severity or which results in one of the following:

- (1) Intraocular bleeding causing loss of vision,
- (2) The need for a transfusion of 2 or more units of red cells,
- (3) Or an equivalent

All hemorrhagic events requiring transfusion of red blood cells should be reported as grade 3 or higher AE per CTCAE v4.03. Events meeting the definition of major hemorrhage will be captured as an event of special interest.

#### **Intracranial Hemorrhage**

Any intracranial hemorrhage adverse event, including subdural hematoma/hemorrhage, epidural hematoma/hemorrhage and intracerebral hemorrhage, of any grade severity, will be captured as an event of special interest.

## **Other Malignancies**

In addition to all routine AE reporting, all new malignant tumors, including solid tumors, skin malignancies and hematologic malignancies, are to be reported for the duration of study treatment and during any protocol-specified follow-up periods including post-progression follow-up for overall survival

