- **Infections:** Fatal and non-fatal infections have occurred with ibrutinib therapy. Grade 3 or greater infections occurred in 14% to 29% of patients. Cases of progressive multifocal leukoencephalopathy (PML) have occurred in patients treated with ibrutinib. Evaluate patients for fever and infections and treat appropriately per current guidelines.
  - **Cytopenias:** Treatment-emergent Grade 3 or 4 cytopenias including neutropenia (range, 19 to 29%), thrombocytopenia (range, 5 to 17%), and anemia (range, 0 to 9%) based on laboratory measurements occurred in patients treated with single agent ibrutinib. Monitor complete blood counts at least monthly.
  - **Atrial Fibrillation:** Atrial fibrillation and atrial flutter (range, 6 to 9%) have occurred in patients treated with ibrutinib, particularly in patients with cardiac risk factors, hypertension, acute infections, and a previous history of atrial fibrillation. Periodically monitor patients clinically for atrial fibrillation. Patients who develop arrhythmic symptoms (e.g., palpitations, lightheadedness) or new onset dyspnea should have an ECG performed. Atrial fibrillation should be managed appropriately, and if it persists, consider the risks and benefits of ibrutinib treatment and follow dose modification guidelines per the USPI for ibrutinib.
  - **Hypertension:** Hypertension (range, 6 to 17%) has occurred in patients treated with ibrutinib with a median time to onset of 4.6 months (range, 0.03 to 22 months). Monitor patients for new onset hypertension or hypertension that is not adequately controlled after starting ibrutinib. Adjust existing anti-hypertensive medications and/or initiate anti-hypertensive treatment as appropriate.
  - **Second Primary Malignancies:** Other malignancies (range, 5 to 16%) including non-skin carcinomas (range, 1 to 4%) have occurred in patients treated with ibrutinib. The

most frequent second primary malignancy was non-melanoma skin cancer (range, 4 to 13%).

- **Tumor Lysis Syndrome:** Tumor lysis syndrome has been infrequently reported with ibrutinib therapy. Assess the baseline risk (e.g., high tumor burden) and take appropriate precautions. Monitor patients closely and treat as appropriate.

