## 1. **Management of Safety Data**

This Study has been designated as an interventional study. As such, all adverse events regardless of causality and special situations excluding those from subjects not exposed to a Janssen Medicinal Product and product quality complaints with or without an adverse event as described in this section will be reported from the time a subject has signed and dated an Informed Consent Form (ICF) until completion of the subject's last study-related procedure (which may include contact for follow-up safety). Serious adverse events will be reported for 30 days after the last dose of study drug.

For the purposes of this study, the Janssen medicinal product is: Ibrutinib (Imbruvica)

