### 2.2. **Adverse Events of Special Interest**

Adverse events of special interest are events that Janssen Scientific Affairs, LLC. is actively monitoring as a result of a previously identified signal (even if non-serious).

These adverse events are:

- **Major Hemorrhage**  
Major hemorrhage is defined as any hemorrhagic event that is Grade 3 or greater in severity or that results in 1 of the following: intraocular bleeding causing loss of vision, the need for a transfusion of 2 or more units of red cells or an equivalent amount of whole blood, hospitalization, or prolongation of hospitalization.
- **Intracranial Hemorrhage**  
Any intracranial hemorrhage adverse event, including subdural hematoma/hemorrhage, epidural hematoma/hemorrhage and intracerebral hemorrhage, of any grade severity, will be captured as an event of special interest.
- **Other Malignancies**  
In addition to all routine AE reporting, all new malignant tumors, including solid tumors, skin malignancies and hematologic malignancies, are to be reported for the duration of study treatment and during any protocol-specified follow-up periods including post-progression follow-up for overall survival.

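### New malignancies must be reported throughout survival follow-up, but after the 30-day safety visit no scheduled contact asks about them and the late-event summary rule excludes them

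*Combined protocol and SAP*

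**What the plan says.** Section 8.1.2 (Other Malignancies) covers all new malignant tumors, whether solid, skin or hematologic. They are "to be reported for the duration of study treatment and during any protocol-specified follow-up periods including post-progression follow-up for overall survival". Appendix C, section 2.2, uses the same terms: they "are to be reported for the duration of study treatment and during any protocol-specified follow-up periods including post-progression follow-up for overall survival". Section 8.1.2 adds that special-interest events, serious or not, "will be reported to Janssen Drug Safety per the SAE reporting timelines".

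Section 6.5 sets out the contacts available for this. A mandatory safety visit takes place about 30 days after the last dose, and adverse events up to that visit are recorded. On confirmed progression or a new anti-cancer therapy, "the subject moves into the survival follow-up phase for 24 months", and patients "should be contacted by telephone every 12 weeks to assess for survival status". In the calendar (section 6.6), footnote j describes a telephone survival check every 3 months and mentions nothing else.

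The reporting and analysis windows are shorter. Section 8.1.1 ends SAE reporting 4 weeks after the last dose, extendable at the investigator's discretion. Appendix C, section 1, says: "Serious adverse events will be reported for 30 days after the last dose of study drug". Section 9.7 (Safety) summarizes adverse events in the 30 days after discontinuation, and lists those after 90 days without summarizing them.

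**The concern.** The protocol sets a longer reporting window for this event than for other safety events, but the schedule contains no step that would find the event in the added part of that window. A site that follows section 6.5 and the calendar to the letter confirms whether the patient is alive and need ask nothing more. Reporting then depends on a patient volunteering a new cancer or the site coming across it in records.

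What is at stake is the completeness of one special-interest event. This cannot be repaired at the analysis stage: if nobody asks during follow-up, an unreported malignancy cannot be told apart from none. The analysis rules add a second loss, because a malignancy reported late has no place in the adverse event summaries.

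**Working it through.** The plan states no figure for this point, so the check sets the duty, the collection steps and the analysis rule side by side.

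1. **Duty.** Sections 8.1.2 and Appendix C 2.2: from treatment through every follow-up period, explicitly including survival follow-up after progression.
2. **Last scheduled adverse event collection.** Section 6.5: the safety visit about 30 days after the last dose. The calendar agrees: the toxicity row is marked at that visit and not in the post-progression column.
3. **Contacts after that.** Section 6.5 and footnote j: a survival call every 12 weeks (footnote j: every 3 months). Among the legible calendar rows, only survival follow-up is marked in the post-progression column. Some rows are blacked out. Footnotes k (archival tissue) and l (blood samples) attach to no legible row, so the hidden rows are probably biospecimens. Section 6.5 and footnote j are themselves legible and name survival only.
4. **SAE cut-off.** Section 8.1.1: 4 weeks. Appendix C: 30 days. Neither exempts this event, although section 8.1.2 requires it to be reported for longer.
5. **Analysis.** Section 9.7, counting from discontinuation: days 0 to 30 are summarized; days 31 to 90 are assigned nowhere; after day 90, events are listed but not summarized.

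Two figures give the scale of the window:

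- Length of survival follow-up: 24 × 30.4375 = 730.5 days.
- Calls at 12-week (84-day) intervals: 730.5 / 84 = 8.7, so about eight or nine calls for a patient followed throughout. None has a specified new-malignancy question.
- The 30-day safety window against that length: 30 / 730.5 = 4.1%. The two periods start from different dates (last dose; progression or new therapy), so this compares lengths only. It is not a share of events.

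**The case against.** The strongest reply is that the duty is already clear and only a written prompt is missing. Section 8.1.2 places this reporting on top of routine adverse event reporting. Section 8.1.1 allows the SAE period to be extended, section 8.2 has adverse events evaluated continuously, and Appendix C carries general adverse event reporting to the last study-related procedure, which may be a safety contact. The CRF and any call script are not in the documents, so sites may in fact ask.

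This stands in part. The duty is not in doubt, and one cannot say that the question will not be asked. But each of these texts restates or extends the duty without supplying a contact that asks. Section 8.1.1 ties the seeking of adverse events to visits, while survival follow-up is a telephone call for which no toxicity item is marked.

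A reader might also infer more than the documents support:

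- *That collection stops with treatment.* It does not: the safety visit records adverse events, so the gap opens after that visit.
- *That the event will certainly be under-counted.* Incidental reports remain possible and the CRF is unseen, so likely passive capture is as far as one can go.
- *That a known number of cancers will be missed.* Section 5.3 gives 5 to 16% for other malignancies and 1 to 4% for non-skin carcinomas. Applied to the synopsis total of 42, that is 42 × 0.05 = 2.1 to 42 × 0.16 = 6.7, and 42 × 0.01 = 0.4 to 42 × 0.04 = 1.7 non-skin. These would be whole-trial totals borrowed from other ibrutinib-treated patients. They do not count missed events, and the share arising after treatment is not given.
- *That second cancers appear late, or that most observation time is follow-up.* The documents say nothing on timing and give no survival estimate for this population. Follow-up ends at death, and entry requires only a life expectancy above 3 months.
- *That the planned tables would claim a rate over the whole follow-up.* They would not, since section 9.7 excludes late events. That exclusion is a fault of its own, and adding a question without changing section 9.7 would leave it in place.

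**Conclusion.** The point holds as an inconsistency between what must be reported and what is scheduled and tabulated. From the safety visit to the end of survival follow-up, new malignancies are likely to be captured only passively. Those more than 90 days after discontinuation would be left out of the summary tables even if reported, and those in days 31 to 90 have no stated place.

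The size of any under-count cannot be computed from the documents. The conclusion rests on reading the visit schedule as complete, and on two assumptions: that the blacked-out calendar rows hold no malignancy item, and that the unseen CRF adds no such question.

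The weight is minor. Safety data are summarized descriptively, and no endpoint, dose-limiting toxicity rule, stopping boundary or sample size depends on this event. It still deserves correction because it changes which data are collected and cannot be put right later.

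**What to change.** - **Sections 6.5 and 6.6.** Add a new-malignancy question (type and date of diagnosis) to each 12-weekly survival contact and to footnote j, with a matching row marked in the post-progression column of the calendar and a CRF field.
- **Section 8.1.1 and Appendix C.** State that reporting of this special-interest event continues past the 4-week and 30-day SAE cut-offs, through the end of survival follow-up.
- **Section 9.7.** Tabulate new malignancies over treatment plus follow-up, separately from the 30-day adverse event summaries, so that the new table does not conflict with the rule for late events.

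The cost is one question and one CRF field in calls already planned, plus one extra table. No visit, procedure or patient is added.
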